2. METHODOLOGY

2.1. Design: Randomized controlled trial of parallel groups.

2.2. Participants:

Sample size and statistical power:

The calculation of the sample size has been made from Objective 1, which focuses on detecting a clinically significant difference in BMI that is the primary outcome measure. Based on previous work that explored weight change in follow-ups after the application of neurocognitive training in people with overweight and obesity (Bazzaz et al., 2017, Kakuschke et al., 2018, Sze et al., 2015), we have selected the smaller sample size (Cohen's $d = 0.46$). With this data, considering the statistical method (models of repeated measures inter and intra subjects), the number of groups ($g = 3$), and assuming an alpha level of 0.05 and a power of 0.80, the resulting sample size calculated with G-Power was 105 participants. To date, no study has conducted a program based on the combination of different neurocognitive tasks that have been proposed as effective for the treatment of obesity, with a 6-month follow-up period. Thus, we opted for a conservative estimate increasing the number of participants to 150. Then, the study could suffer a sample loss of 30% from the initial session to the follow-up at 6 months and the statistical power would be still guaranteed. Previous studies that explored neurocognitive training to lose weight with different follow-up periods have showed smaller attrition rates [i.e., 16% in a 3-month follow up (Carbine et al., 2021); 12.3% in a 2-month follow-up (Forman et al., 2019); 3.4% in a 6-month follow-up (Lawrence et al., 2015)].

Participants:

The participants ($N=150$) will be randomly allocated to three groups: experimental group (neurocognitive intervention; $n=50$), active control group (sham intervention; $n=50$), and control group (treatment as usual; $n=50$).

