People between 18 and 55 years old will be candidates to participate in the study, with a good command of the Spanish language, a range of BMI between 25 and 39.9 kg/m², and with at least two electronic devices available (one tablet, computer or smartphone to attend the online meeting and one smartphone with a gyroscope to do the training with the apps). All candidates will be screened for medical and psychological disorders and excluded if they have: (i) traumatic, digestive, metabolic or systemic disorders that affect the central nervous system, autonomic or endocrine, (ii) cardiovascular or any other disorders that prevent physical exercise; (iii) psychopathological disorders or presence of severe symptoms in the Depression Anxiety and Stress Scale-21 (DASS-21); (iv) eating disorders or presence of criteria in the Questionnaire on Eating and Weight Patterns-5 (QEWP-5); (v) pharmacological or any other kind of treatment for losing weight at present; (vi) candidates for bariatric surgery; (vii) food conditions that could interfere with the stimulus of the program (allergies, sprue, vegetarianism, veganism); (viii) current pregnancy or breastfeeding (or expected pregnancy in the following six months); (ix) weight loss $>5\%$ on the 3 months previous to the program; (x) use of medication that affects weight; (xi) frequent use of alcohol or other drugs that affects food intake.

Sampling context:

The recruitment will be carried out through social media and the web of the project.

Randomization and blinding:

A randomization (minimization) through the software Minimizer® will be performed to avoid imbalances between the groups in age, sex, and BMI (Stout et al., 1994). The psychologists that conduct the assessments (screening, evaluation sessions and follow-ups) will be blinded to the group allocation during the whole project. Moreover, since all assessments will be computerized and online, they are not subject to the biases of the evaluator. Further, all participants will be blind to their condition. Also, the people who perform the statistical analyses will be blind to the condition of the groups, through the coding of the interventions. Only the therapist performing the interventions will not be blind to the allocation of the participants.

2.3. Interventions:

Pre-treatment interventions (all groups).

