2.4. Outcome measures:

Note: The measures have been selected attending to ADOPT (Accumulating Data to Optimally Predict Obesity Treatment), to generate evidence about the efficacy for obesity interventions (MacLean et al., 2018). These measures are marked with an asterisk (*).

(1) Main outcome measure

- a. BMI*: Height and weight will be measured to determine BMI. The weight and height for the calculation of the BMI (kg/m²) will be obtained with a pharmacy digital scale

BMI will check for the results of the whole program (the 4 intervention sessions), and will be registered weekly from session 1 to post-treatment assessment, and will be also registered at follow-ups (3- and 6-months post-treatment). In addition, the week before the pre-treatment assessment session, it will be recorded daily to obtain the baseline weight and then averaged.

(2) Secondary outcomes (changes in cognitive measures, changes in eating and physical exercise behaviors and body measures).

(2.1) Changes in cognitive measures.

- a. Approach-avoidance bias: The approach-avoidance bias will be calculated before and after the 1-week training with the Tilt Task app. Participants should zoom in or out the appetizing and healthy food images that appear on the screen, depending on the presentation format of the image (horizontal or vertical). Approach and avoidance trials will be 50% for each type of image (healthy vs. unhealthy). The average reaction time of the approach (pull) and avoidance (push) trials will be subtracted separately for healthy and unhealthy foods, with the positive and

negative scores representing approximation and avoidance bias, respectively (see Kakuschke et al., 2018 for a full description).

- b. Food inhibition assessment: Using the Food Trainer task, reaction time for the high-calorie and low-calorie foods paired 50% with the go and 50% with the no-go signal will be measured before and after the 1-week training with the app. The average response time for go and no-go items will be calculated according to the type of images (appetizing and healthy foods), and commission errors will be recorded (see Lawrence et al., 2015).

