Based on Cohen's (1992) rule of thumb, clinical significance of change will be reflected by medium within-group effect sizes ($d \geq .5$).

Mediation and/or moderation analysis will be carried out to study the role of variables related to cognition, affect, stress and non-homeostatic food intake, motivation and personality on the program outcome measures.

In addition, possible differences in the program outcomes will be assessed based on sex and weight classification (overweight and obesity -type I and type II).

All the analyses described will be carried out following an intention to treat strategy (ITT) and analysis per protocol (PP). Corrections will always be considered to control for multiple comparisons.

- For objective 4, the average cost and effectiveness (BMI and QALY) for the 3 groups (intervention, sham and treatment as usual) will be estimated. The ratios of incremental cost effectiveness and incremental utility cost will be calculated as the cost and effectiveness difference (BMI and QALY) for the 3 groups. All the analyses will be carried out according to the methodological recommendations for Spain (López-Bastida et al., 2010). The perspective of the health system will be used, including only direct costs. The uncertainty of the results will be carried out through various deterministic sensitivity analysis (AS) and a probabilistic one using nonparametric bootstrapping methods of 1000 iterations (Luce et al., 2001) that will allow to represent the cost-effectiveness plane and the Acceptability curve. The AIP will estimate the variation that the introduction of neurocognitive training would imply for the budget of the public health system, based on the estimated costs of the alternatives compared and the estimated number of patients expected to benefit from the program. Likewise, univariate and multivariate AS will be performed to analyze different budgetary scenarios based on a possible variation in the cost variables and number of beneficiary patients.

**Only in experimental and active control groups (what is not in italics is done by all three groups: experimental, active control, and control) //* Assessment task

Figure 1: Procedure of the program.

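### Variation of the programme's effect with body weight is assessed only by weight class; a single arm-by-continuous-baseline-BMI test would use the data better if the effect varies smoothly

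*Combined protocol and SAP*

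**What the plan says.** Near the end of section 4 (Data analysis plan), after the sentence on mediation and moderation, the plan adds that "possible differences in the program outcomes will be assessed based on sex and weight classification (overweight and obesity -type I and type II"). It names no interaction test, class cut-points or expected class sizes. The mediation/moderation sentence covers "variables related to cognition, affect, stress and non-homeostatic food intake, motivation and personality on the program outcome measures"; baseline BMI is not on that list. The class sentence is therefore the only stated analysis of whether results differ by body weight.

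A continuous baseline is available. Section 2.2 admits "a range of BMI between 25 and 39.9" kg/m². Section 2.4 says of BMI in the week before the pre-treatment assessment that "it will be recorded daily to obtain the baseline weight and then averaged". Section 2.2 also uses BMI in the minimization, "to avoid imbalances between the groups in age, sex, and BMI". That balances the arms but does not fix how many people fall in each class.

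**The concern.** Cutting a measured covariate into three classes treats people just either side of a limit as different, and people at opposite ends of one class as the same. With three arms, an interaction with three classes costs (3−1)×(3−1) = 4 degrees of freedom; an interaction with one continuous slope costs 3−1 = 2. If the benefit rises or falls gradually with BMI, the class analysis has less chance of showing it. Estimates in whichever class turns out smallest will be imprecise and easy to over-read. The question matters for deciding whom the programme suits, and a trial of 150 people in three arms has little information on it to spare.

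**Working it through.** **Inputs from the documents.** Section 2.2 gives N = 150, 50 per arm; tolerated loss 30%; alpha 0.05; target power 0.80; d = 0.46; BMI 25–39.9. Section 4 gives the three classes. The plan has no figure for any weight class, so there is nothing to reproduce on that point. The step from 105 to 150 does reproduce: 105/(1−0.30) = 150, so 35 per arm remain after full loss.

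**Assumptions, not in the documents.** Cut-points 30 and 35; an effect linear in BMI; an F test of arm by class; and a set of BMI distributions.

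**Step 1: information kept.** The share of BMI variance kept by the classes is R² = Σ pₖ(mₖ−μ)²/σ², where pₖ and mₖ are the share and mean BMI of class k. For a uniform distribution over 25–40, the total variance is 15²/12 = 18.75 and the within-class variance is 5²/12 = 2.08. So R² = 1 − 2.08/18.75 = 0.89.

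**Step 2: power.** The noncentrality giving 80% power for F(2, N−6) is λ = 9.84 at N=150 (9.93 at N=105). Through the classes the same gradient has noncentrality λR², tested on F(4, N−9). For the uniform case at N=150, 9.84×0.889 = 8.75, which gives 63% power. The 4-df test needs a noncentrality of 12.34 for 80%, so the required-N ratio is 12.34/8.75 = 1.41. Both models are given the same residual variance, which slightly favours the class test.

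| Assumed BMI distribution | Share in type II | Type II per arm (50 / 35 per arm) | R² | Class-test power | N ratio |
|---|---|---|---|---|---|
| Uniform, 25–39.9 | 33% | 16.4 / 11.5 | 0.89 | 63% | 1.41 |
| Skewed to overweight (scaled beta 1.2, 2.2) | 11% | 5.7 / 4.0 | 0.84 | 60% | 1.50 |
| Truncated normal, centre 31, SD 4 | 16% | 7.9 / 5.5 | 0.83 | 60% | 1.51 |
| Exponential decline, scale 4 | 6% | 3.0 / 2.1 | 0.81 | 59% | 1.54 |
| Truncated normal, centre 29, SD 4 | 8% | 3.8 / 2.7 | 0.80 | 58% | 1.56 |

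The most extreme case tried, a truncated normal centred at 28, sets the lower limit on class size: 5% in type II, 2.5 per arm. It has R² = 0.78, which gives 57% power and a ratio of 12.34/(9.84×0.782) = 1.60. A uniform distribution run to 40 instead of 39.9 puts about 17 per arm in type II.

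**Step 3: away from the 80% anchor (N=150).** If the continuous test has 30% power, the class test has 19–20%. If it has 20%, the class test has 13–14%. The N ratio does not change.

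**Step 4: if the effect is not linear.** Fix the class test at 80% power. For a step at 30, the linear test has 72–74% (uniform and skewed cases). For a step at 35 it has 72% (uniform), 52% (skewed) or 44% (centre 29). If only the middle class differs, it has 5% (uniform) or 25% (skewed).

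**Step 5: a joint linear-plus-quadratic test.** This also costs 4 df. With a truly linear effect and λ = 9.84, power falls from 80% to 69%.

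**Step 6: contrasts inside type II.** Two-arm power at d = 0.46 is Φ(0.46√(n/2) − 1.96). For n = 17 per arm, 0.46×2.92 − 1.96 = −0.62, so 27%. It is 15% at n = 8, 10% at 4 and 8% at 3, against 63% at 50 per arm. The normal approximation is optimistic at the smallest n.

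**The case against.** The strongest reply is that classes are the better choice if the effect changes at a class limit, and nothing in the documents favours a straight line. Step 4 shows that the ranking then reverses, in places by a wide margin. This stands, and it is the real price of the fix.

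Second, the sentence names no test. The 4-df interaction is an inference, and separate tests within classes are not stated either. Section 4 also says that the inferential methods will follow the nature of the data, so a continuous analysis is not ruled out. This stands as a limit on the claim. It does not remove the point: the only stated form is the classes, and an analysis that is merely permitted is not prespecified.

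Third, 80% is an arbitrary anchor. At realistic power for an interaction in this trial, both tests would usually miss a gradient (step 3). This stands; the ratio of sample sizes is the steadier summary.

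Fourth, section 4 says that corrections for multiple comparisons will be considered. That covers class comparisons in a loose way, but it does not restore the lost information.

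A reader might also infer that the plan leaves a very small type II group. The documents do not support that. They give no BMI distribution, class sizes or cut-points, and under a uniform distribution type II is about a third of the sample.

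**Conclusion.** The point holds as a cheap improvement to a secondary analysis. The plan collects a good continuous baseline BMI and states only a three-class analysis of effect variation by weight. Under linear moderation and cut-points of 30 and 35, an arm-by-class test has about 58–63% power where the continuous test has 80% (57% in the most extreme distribution tried), or needs 1.4–1.6 times the participants. These are conditional figures, not a forecast of this trial's power, which is probably low for either test. They do not show that a continuous test is better whatever the shape of the effect.

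On class size, the most that can be said is that type II may be small: about 2–3 to 17 per arm at N=150. Two-arm contrasts inside it would have at most about 27% power at the plan's d of 0.46 over that whole range. The primary test, the sample size and the main conclusions are unaffected.

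**What to change.** In section 4, state that moderation by body weight will be tested once, by the interaction of arm with continuous baseline BMI (2 df for three arms). Because baseline BMI is also the first of the four BMI measurements, fit this for BMI with later BMI, or change, as the dependent variable and baseline BMI as a covariate. Add a quadratic BMI term by arm only as a separate sensitivity check, not as part of a joint test. State the class cut-points, and show effect estimates with confidence intervals by weight class as description.

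The cost is a few sentences of SAP wording, with no change to N, visits, measurements or the primary test. The statistical cost is lower power if the true effect is a step or is not monotone in BMI. The class display and the quadratic check would help to reveal such a pattern, but they would not recover that power.
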